### **3.5 Identification of Source Data**

Electronic medical records will be maintained via a RedCAP database for consecutive and prospective collection of data.

Efficacy measures used in the study include: clinical assessments will include serial brain MRI, EEG, anti-seizure drug levels and subject self-assessment at clinical follow-up; Neurological Disorders Depression Inventory for Epilepsy (NDDI-E), assessment for screening of depression PHQ-9;Montreal Outcome Cognitive Assessment (MOCA); Clinical Global Impression of Change (CGIC) score; Columbia –Suicide Severity Rating Scale. Seizure calendars performed at 2 months prior to initiation of therapy or adequate reliable historical baseline, and then monthly during study; and QOLIE-31, (see schedule of events for frequency of assessment).

Anatomic brain MRI with perfusion scanning/gadolinium will be obtained at 3 months and then every 3 months, to examine the correlated progression of brain tumor, or the absence of tumor. Laboratory studies will be employed before and after PER initiation. EEG will be obtained at baseline and at 3 months and 12 months to identify changes in background activity (e.g. diffuse slowing) and epileptiform discharges to correlate with focal seizure presence vs absence. Neuropsychological batteries will determine the presence or absence of significant anxiety, depression or cognitive changes over time and quality of life inventory will be obtained at the beginning, intermediate and end of the trial.

The following source data will be directly recorded on the Case Report Form (CRF):

- A comprehensive History and Physical examination and Neurological examination will occur at the initial screening/baseline.
- Clinical visitation will occur at screening/baseline, 3, 6, and 12 months.

Survey questionnaires will be obtained at baseline, 3, 6, 9, and 12 months. The following source data will not be directly collected in the Case Report Form (CRF), but will be captured in supportive documentation (study source documents, EMR):

- Laboratory studies will be employed at baseline and at each clinical visit after PER initiation.
- Brain tumor tissue will be assessed for the usual molecular markers (i.e., IDH-mutant vs wildtype, MGMT methylation, ARX).
- 12-lead ECG will be obtained at baseline and as clinically indicated
- Anatomic brain MRI with and without gadolinium will be obtained at baseline and follow-up brain MRI at 3 months and 6 months during PER use.

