**Schedule of Events**

Procedure	Screening & Baseline Visits 		Titration Phase 				Treatment Phase 								
			Day 7	Day 14	Day 21	Day 30	Day 60	Day 90	Day 120	Day 150	Day 180	Day 210	Day 240	Day 270	Day 300
Visit Day	Day 0-6														
Visit Number	1 	2 	3	4	5	6	7 	8	9 	10 	11	12 	13 	14 	15
Informed Consent	X														
Inclusion and Exclusion Criteria check 	X														
Medical/Surgical History	X		X	X	X	X	X	X	X	X	X	X	X	X	X
Concomitant medications	X		X	X	X	X	X	X	X	X	X	X	X	X	X
Neurological Examination	X					X		X			X				X
Physical Examination	X					X		X			X				X
Clinical Labs 	X							X			X				X
Historical Anatomical Brain MRI review 	X														
Anatomical Brain MRI 	X							X			X				X
Historical EEG review 	X														
Standard EEG 	X							X			X				X
Neuropsychology visit	X							X			X				X
NDDI-E	X		X	X	X	X	X	X	X	X	X	X	X	X	X

PHQ-9	X	X	X	X	X	X	X	X	X	X	X	X	X	X	X
MOCA	X	X	X	X	X		X			X					X
CGIC	X	X	X	X	X		X			X					X
C-SSRS	X	X	X	X	X	X	X	X	X	X	X	X	X	X	X
QOLIE-31	X	X	X	X	X	X	X	X	X	X	X	X	X	X	X
Urine Pregnancy Test	X														
Dispense Seizure Diary	X	X	X	X	X		X			X					
Seizure Diary Review		X	X	X	X	X	X	X	X	X	X	X	X	X	X
Adverse Event Assessment	X	X	X	X	X	X	X	X	X	X	X	X	X	X	X
Dispense Study Drug		X	X	X	X		X			X					
Study Drug Accountability		X	X	X	X		X			X					X

Clinical assessments (MRI, EEG, clinical labs, and anti-seizure drug levels) performed before or after scheduled follow-up if deemed clinically necessary outside of the study protocol.

±3-day tolerance window

CMP to include the following blood tests: albumin, blood urea nitrogen, calcium, carbon dioxide, chloride, creatinine, glucose, potassium, sodium, total bilirubin and protein, and liver enzymes (alanine aminotransferase, alkaline phosphatase, and aspartate aminotransferase).

 Screening and Baseline are preferred to occur consecutively on the same day but, if this is not feasible for the patient, the Baseline Visit procedures can occur any time after screening *and* before Day 7..All screening and baseline results must be available for review prior to dispensing study drug on day 7.

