 Any development to the patient's history affecting their standing within the inclusion and exclusion criteria will be continually assessed throughout the study.

As needed and only for PER arm.

Baseline MRI and EEG performed only if one has not been performed within three months prior to baseline. , otherwise historical MRI and/or EEG will be reviewed .

Visits 7, 9, 10, 12, 13, and 14 will be completed as Phone Visits (PV).

±7-day tolerance window

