#### Handling of Missing Data

Study data will be collected and managed using REDCap electronic data capture tools hosted at Mayo Clinic. All data requested on the Case Report Form (CRF) will be recorded for each participant. A standardized CRF will be generated by REDCap. For any data query, the Principal Investigator and Investigators will meet to clarify the data queried and make corrections based on consensus. Once the study is completed, the Principal Investigator will randomly select 3 participants and compare the data documented for each on the CRF with what is entered into the REDCap database. If there is any discrepancy, the Principal Investigator and/or Investigators will cross-reference all 20 patients to ensure accuracy.

**Primary Hypothesis:** We hypothesize that perampanel will lead to a significant reduction in seizure frequency for adult patients with brain tumor-related seizures associated with high-grade glioma.

We will compare seizure frequency before and 3 months after treatment with monotherapy and adjunctive PER and use descriptive statistics to demonstrate differences in responders. A P-value < 0.05 will be used to reflect statistical significance.

**Secondary Hypothesis 1:** We hypothesize the progression of brain tumor (comparing 4 and 8 mg/d of perampanel) based upon fusion by comparing baseline brain MRI and MRI at 12 months will be less for IDH-mutants.

We hypothesize there will be minimal or no change in neurocognitive function from 0 to 3 months on Montreal Outcome Cognitive Assessment (MOCA; higher scores indicating greater function); and the Clinical Global Impression of Change (CGIC; scores from 1 to 7, with lower scores indicating greater improvement and a score of 4 indicating no change).

Chi-square and Student T-test will be used to measure differences in assessment and change during the study period. A P-value < 0.05 will be considered significant.

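### Secondary Hypothesis 1 measures tumour progression on a 12-month MRI that the Schedule of Events lacks, and 7.2 does not carry the PER versus alternate-ASD comparison into that analysis

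*Combined protocol and SAP*

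**What the plan says.** **The analysis.** Secondary Hypothesis 1 sits in 7.2, under the subheading on missing data. It predicts that progression, comparing 4 and 8 mg per day of PER, "based upon fusion by comparing baseline brain MRI and MRI at 12 months will be less for IDH-mutants". The test sentence that follows gives chi-square, t-test and a 0.05 threshold, but names no groups.

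**The scans.** The Schedule of Events marks anatomical brain MRI at baseline, Day 90 (Visit 8), Day 180 (Visit 11) and Day 300 (Visit 15). Visit 15 is the last visit of any kind. The treatment-phase columns carry two window footnotes, a ± "3-day tolerance window" and a ± "7-day tolerance window". Footnote 1 covers MRIs "performed before or after scheduled follow-up if deemed clinically necessary outside of the study protocol". Section 3.5 gives two other timetables: MRI "will be obtained at 3 months and then every 3 months, to examine the correlated progression of brain tumor, or the absence of tumor", and then "follow-up brain MRI at 3 months and 6 months during PER use". It also says: "Clinical visitation will occur at screening/baseline, 3, 6, and 12 months". Sections 6.2, 6.8 and 6.11 (Visits 2, 8 and 11) specify an MRI with volume measurement. Section 6.15 (Visit 15) speaks only of the MRI being reviewed.

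**The objectives.** The Study Summary and Section 2 both set progression on PER against alternate ASDs. The IDH objective in both places concerns seizure reduction. The Reference therapy row of the Study Summary makes standard ASDs the reference for all comparisons.

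**The concern.** There are two separate faults.

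1. **Timing.** The outcome is defined on a scan that the visit schedule does not provide, and the sections that mention MRI timing disagree. A site following the Schedule ends at Day 300, while an analyst following 7.2 looks for a scan about two months later. Someone must then decide, with data in hand, which scan counts.

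2. **Contrast.** The progression hypothesis compares IDH groups and PER doses. Neither is the comparison in the objective. Section 1.1 itself links IDH mutation to prognosis, so IDH groups may progress differently whatever ASD they take. PER dose is flexible and is settled after baseline. A clear IDH or dose result would leave the question about PER and progression unanswered, and the estimate that would address it is not specified.

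**Working it through.** No sample-size or power figure bears on this point: Section 7.1 says the study is not powered for effectiveness. The check is a comparison of passages and some calendar arithmetic.

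**MRI time points, side by side**

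| Source | MRI time points |
|---|---|
| 7.2, Secondary Hypothesis 1 | baseline, 12 months |
| Schedule of Events | baseline, Days 90, 180, 300 |
| 3.5, first statement | 3 months, then every 3 months, no stated end |
| 3.5, second statement | baseline, 3 and 6 months |
| 6.2, 6.8, 6.11, 6.15 | completed with volume measurement at Visits 2, 8, 11; reviewed at Visit 15 |

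No two follow-up timetables in the first four rows match. The wording at Visit 15 is also used at Visit 5 (6.5), where the Schedule marks no MRI, so it does not settle whether the final scan is measured like the others.

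**Gap to 12 months**
- Nominal: 365 − 300 = 65 days.
- With +3 days: 365 − 303 = 62 days.
- With +7 days: 365 − 307 = 58 days.
- Counting 12 months as 360 days: 360 − 307 = 53 days at the widest window.

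No stated window brings Visit 15 to 12 months.

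**Fit with the treatment period.** The Study Summary objective refers to 40 weeks of PER, which is 280 days. From first dispensing on Day 7 this ends on Day 7 + 280 = 287. If 2 to 4 weeks of titration come first, it ends on Day 7 + 14 + 280 = 301 to Day 7 + 28 + 280 = 315. If titration starts at enrolment (4.3), taken as Day 0, and the 40 weeks include it, treatment ends on Day 280. On all of these readings Day 300 lies near the end of treatment, and Day 365 falls 50 to 85 days after it (365 − 315; 365 − 280).

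**Scan interval.** Footnote 7 reads: "Baseline MRI and EEG performed only if one has not been performed within three months prior to baseline". Otherwise a historical scan serves. Taking three months as 90 days, baseline on Day 0–6 and Visit 15 on Day 293–307, the baseline-to-final interval runs from 293 − 6 = 287 to 307 + 90 = 397 days. A scheduled 12-month scan would not remove this spread, so intervals need reporting whichever end point is chosen.

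**Contrast, side by side**

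| Source | Outcome | Comparison |
|---|---|---|
| Study Summary and Section 2 | progression | PER versus alternate ASD |
| Study Summary and Section 2 | seizure reduction | IDH-mutant versus wildtype, on PER |
| 7.2, Secondary Hypothesis 1 | progression | IDH status; 4 and 8 mg per day |

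The third row takes its outcome from the first objective and its grouping from the second. No stated objective concerns IDH and progression.

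**Precision of the intended comparison.** Section 4.3 gives 10 subjects per group. The 95% CI half-width for a difference in means, in SD units, is t(0.975, 18) × √(1/10 + 1/10) = 2.101 × 0.447 = 0.94. This assumes that all 20 subjects have both scans; missing final scans widen it.

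**The case against.** A fair defence has four parts.

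**A 12-month scan can be read into the text.** Three-monthly MRI and a 12-month clinical visit in 3.5, with 12 months of participation in the Study Summary and 3.3, together imply one. This stands. A reader might infer that no part of the protocol could supply the scan; the documents do not support that. What they show is a conflict between the Schedule, which sites work from, and the text.

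**The comparator is stated.** The Reference therapy row is general, and both statements of the objective name alternate ASDs. The dose wording may also be shorthand for the 4–8 mg range. This stands too, so it would be wrong to say that the plan lacks a comparator for progression. But 7.2 names a different contrast for this outcome, and reading the doses as a range still leaves no between-group comparison or effect measure there.

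**A significant IDH result would not be an error.** A reader might infer that such a result is a false positive. It is not: the hypothesis predicts less progression in IDH-mutants, so rejection when that is true is correct. Nor does 7.2 claim that the IDH contrast isolates a PER effect. The fault is that it answers a different question from the objective.

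**The stakes are small.** This is one secondary hypothesis in an unpowered, non-randomised pilot of 20. That limits the severity. It does not excuse an outcome whose time point is contradicted, particularly in a pilot meant to inform a larger trial.

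**Conclusion.** Both faults hold and should be corrected. The scan named in 7.2 is not in the Schedule of Events: the last scheduled MRI falls 65 days before Day 365, or 58 days at the latest permitted date (53 if 12 months means Day 360). Section 3.5 disagrees with both, and 6.15 leaves the final measurement unclear. Separately, 7.2 does not carry the stated PER versus alternate-ASD comparison into the progression analysis, so following it as written would not answer the secondary objective.

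The timing finding rests on the Schedule's columns and windows as printed. The contrast finding needs no assumption about the size of any IDH or PER effect. The point does not bear on the primary endpoint, and it does not imply that the study ought to be powered for progression.

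**What to change.** 1. **One scan.** Reconcile the MRI time points in 3.5, 6.15, 7.2 and the Schedule, and tie the progression analysis to one scheduled MRI. Day 300 needs no added visit; keeping 12 months means adding that scan to the Schedule. Define the measurement: 7.2 speaks of fusion and the visit text of volume, and nothing links the two. State that it is made in the same way at baseline (historical scans included) and at the final scan, in both groups.

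2. **The intended contrast.** In 7.2, make the progression analysis PER versus alternate ASD, as a difference in change from baseline with a 95% CI. Label it descriptive, because the treating physician chooses the arm (4.3) and there are about 10 subjects per group. Show IDH status by group. Report the IDH and dose contrasts as exploratory, not as evidence of a PER effect.

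3. **Missing final scans.** Report by group how many subjects lack the final MRI, separating deaths from withdrawals. Section 3.4 uses the latest data before death; if that rule is applied here, show those subjects separately with their scan intervals, because a short interval can understate progression.

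**Cost.** A small amendment and consistent reads of scans already planned, or one extra scan per subject if 12 months is kept. The sponsor gives up a confirmatory-looking IDH or dose claim on progression. The between-group estimate that replaces it will be imprecise and open to confounding by the choice of arm.

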### **3.4 Primary Endpoints**

- A. The number of patients with a high-grade glioma who achieve a > 50% reduction in focal seizures with PER 4 mg daily after failing 1 or more ASDs at 3 and 6 months.
  1. The overall survival of patients with high-grade glioma treated with PER at 3 months.
  2. Decline in neuropsychological function at 6 months.

All comparisons will use intent to treat model for patients initiated or exiting PER therapy. In event of patients not surviving till 12 months, most recent data prior to death will be used for correlation.

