### 4.2 Exclusion Criteria

1. Subject has serious cardiac, respiratory, renal, gastrointestinal, hematologic, or other medical condition as determined by the investigator to potentially interfere with the study
2. Subjects with glioblastoma not following Stupp protocol for treatment of glioblastoma.
3. History of status epilepticus in the 6 months prior to screening or a history of seizure clusters progressing to status epilepticus.
4. Past medical history of drug and/or alcohol abuse
5. Pregnant or breast-feeding
6. Subjects treated with PER prior to baseline
7. Prior felony conviction disclosed by the patient or previously stated in medical record.
8. History of violent behavior
9. Clinically significant laboratory abnormality at screening or baseline visits, as determined by the investigators
10. Use of an investigational drug or device within 20 days prior to treatment Day 1
11. Repeated radiation therapy for tumor regrowth
12. Subjects that plan to undergo tumor resection on or after baseline visit
13. Uncontrolled psychiatric disorder at baseline

14. Subjects who report active suicidal attempts or suicidality including subjects with a history of suicide attempts or suicidality determined to be clinically significant by investigators at screening.

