### **6.11 Visit 11**

Seizure frequency is assessed. Seizure Diary is reviewed. Medical history and physical examination are performed. Neurological examination is performed. An MRI of the brain with volume

Revised 23NOV2022

measurement is completed. An EEG is completed. PHQ-9, NDDI-E, MOCA, CGIC, C-SSRS and QOLIE-31 are completed. Neuropsychological follow-up assessment. Dispense study drug to participants in Group A (PER arm).

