### **7.3 Subject Population(s) for Analysis**

Analysis of the protocol-compliant population will be conducted. 3, 6, and 12 month evaluability will be assessed based upon the severity of the glioma disease process associated with brain tumor-related focal seizures and risk of imminent death from high-grade malignant primary brain tumor.

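### Tumour progression is judged from two scans with no analysis rule for regrowth treated in between, so a patient who progressed can be scored on a post-treatment scan or dropped

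*Combined protocol and SAP*

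**What the plan says.** Secondary Hypothesis 1, which sits under the missing-data heading of Section 7.2, compares two scans: progression "based upon fusion by comparing baseline brain MRI and MRI at 12 months will be less for IDH-mutants". It gives no threshold, response criteria or time-to-event definition. The secondary objectives also compare MRI progression with alternate anti-seizure drugs.

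The Schedule of Events places anatomical MRI at baseline, Day 90, Day 180 and Day 300. Section 6 specifies volume measurement at Visits 2, 8 and 11; Visit 11, for example, calls for "An MRI of the brain with volume" measurement. For Visit 15 (Day 300), Section 6.15 says only that the MRI is reviewed.

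Three passages touch on treated regrowth:
- Exclusion 11: "Repeated radiation therapy for tumor regrowth".
- Exclusion 12: "Subjects that plan to undergo tumor resection on or after baseline visit".
- Schedule of Events, footnote 5: "Any development to the patient's history affecting their standing within the inclusion and exclusion criteria will be continually assessed throughout the study".

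None of them says what happens to the patient's data, and Section 4.4.1 on withdrawal adds nothing on this.

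The only substitution rule concerns death: "In event of patients not surviving till 12 months, most recent data prior to death will be used for correlation" (Section 3.4). On the analysis set, Section 3.4 says "All comparisons will use intent to treat model for patients initiated or exiting PER therapy", whereas Section 7.3 says "Analysis of the protocol-compliant population will be conducted" and ties evaluability at 3, 6 and 12 months to the severity of the glioma and the risk of imminent death.

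**The concern.** A baseline-to-final comparison measures progression only if nothing has removed or shrunk the tumour in between. If regrowth seen at Day 180 leads to surgery or further radiotherapy, the final scan reflects the tumour and the intervention together, and the Day 180 evidence is not used.

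The patient's data then follow one of two routes. Under intent to treat, the patient stays in and is scored on a post-intervention scan. Under the protocol-compliant set, or through the severity-based evaluability judgement, the patient may leave the analysis because of the progression. The plan does not say which route applies.

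Progression by IDH status is a stated hypothesis tested at P < 0.05, and progression against alternate drugs is a secondary objective. The treating physician chooses the arm (Section 4.3), so treated regrowth need not be balanced between arms. The pilot is meant to inform a larger trial, which could inherit the definition.

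**Working it through.** The plan gives no progression rate, tumour volume, standard deviation or re-operation frequency, so there is no figure of its own to reproduce. The check has two parts.

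**1. Which passage would govern such a patient?**

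| Event after baseline | Passage that touches it | Consequence for analysis |
|---|---|---|
| Unplanned resection | Exclusion 12 (planned resection), footnote 5 | None stated |
| Repeat radiotherapy | Exclusion 11, footnote 5 | None stated |
| Changed antitumour treatment for regrowth | No analysis rule found | None stated |
| Death before 12 months | Section 3.4 | Most recent data used |

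Only death has a rule.

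**2. What would a two-scan comparison return?**

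Everything here is assumed: percent volume change as the measure, 20 mL at baseline, 40 mL at the scan before surgery, a share *e* of the 40 mL removed, and *m*-fold regrowth by the final scan.

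Change at progression = (40 − 20)/20 = +100%.

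Final change = [40 × (1 − *e*) × *m* − 20]/20.

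| Removed | *m* = 1.25 | *m* = 1.5 | *m* = 2 |
|---|---|---|---|
| 50% | 25 mL, +25% | 30 mL, +50% | 40 mL, +100% |
| 70% | 15 mL, −25% | 18 mL, −10% | 24 mL, +20% |
| 90% | 5 mL, −75% | 6 mL, −70% | 8 mL, −60% |

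Five of the nine cells are below baseline and four are not. Eight understate the +100% seen before surgery; in the ninth (50% removed, then doubling) nothing is lost.

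Shift in a group mean = (*k*/*n*) × (100 − final change), for *k* such patients among *n*. With *k* = 2 and *n* = 10:
- Smallest: 0.2 × (100 − 100) = 0 points.
- Largest: 0.2 × (100 + 75) = 35 points.

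With *k* = 1 the range is 0 to 17.5 points.

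A second set of assumptions has no regrowth after surgery. If the tumour grows by a fraction *g* and a share *e* of the result is removed, the final change is (1 + *g*)(1 − *e*) − 1. This is negative only when *e* exceeds *g*/(1 + *g*): 20% for *g* = 0.25, 33% for *g* = 0.5 and 50% for *g* = 1. Any removal leaves the final value below the value at progression.

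**Chance that the case arises.** If a proportion *p* of patients has such an intervention, the chance of at least one among 20 is 1 − (1 − *p*)^20. That is 64% at an assumed *p* of 5% and over 99% at 30%. Among 10 patients it is 40% and 97%.

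**The case against.** The exclusions and footnote 5 can be read more generously. Exclusion 11 has no time limit. Exclusion 12, read with continual reassessment, could take in surgery first planned during follow-up. It would therefore be wrong to say that the plan ignores these events. What stands is narrower: it states no consequence for the analysis. If the consequence is removal, patients are lost because they progressed.

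A reader might infer that every patient operated on for regrowth is recorded as having a shrinking tumour. The documents do not support that. Four of the nine illustrative cells end at or above baseline, and the patient may be dropped instead of scored. The text also specifies a 12-month MRI and fusion, without defining the result as percent change in volume, and Section 6.15 does not state a volume measurement at Day 300.

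A reader might also infer a known bias in favour of one arm or IDH group. That is not supported either. IDH group sizes and intervention rates are not given, and imbalance is possible but not shown. The point shifts above are for a group of 10, whereas the hypothesis itself concerns IDH status and two perampanel doses.

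Finally, this is a secondary hypothesis in a pilot of 20 that Section 7.1 says is not powered. That limits the priority but does not supply the missing rule.

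**Conclusion.** The concern holds as a gap in the analysis rule. Progression is judged from two scans, the intermediate scheduled scans are unused, and treated regrowth has no stated handling. The two statements on the analysis set leave open whether such a patient is mis-scored or excluded; either can hide observed progression.

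The size can only be illustrated: 0 to 35 percentage points in a group mean for two affected patients of 10, with every volume assumed. The frequency of the event and the direction of any between-group bias cannot be determined from the documents. Priority is low to moderate.

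**What to change.** Amend Secondary Hypothesis 1 and Section 7.3 as follows:

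1. Define progression explicitly, using all scheduled MRIs.
2. Count a patient with tumour resection, repeat radiotherapy or changed antitumour treatment for regrowth after baseline as progressed on the date of the scan that prompted it.
3. In any volume comparison, use that patient's scans up to and including the last one before the intervention.
4. Name one analysis set for this hypothesis, reconciling Sections 3.4 and 7.3, and keep these patients in it.
5. Report their number by arm and by IDH group.
6. Show the raw baseline-to-final change as a sensitivity analysis.
7. Reconcile the 12-month MRI with a schedule that ends at Day 300, and state in Section 6.15 that volume is measured at Visit 15.

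The cost is analysis-plan wording and one CRF field for the date and type of tumour treatment. The scans are already scheduled, and the Schedule of Events already collects medical and surgical history throughout follow-up. The drawback is a shorter volume interval for these patients.

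### Tumour progression is a two-scan change to an unscheduled 12-month MRI, with two conflicting rules for patients who die first, and neither rule counts death as progression

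*Combined protocol and SAP*

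**What the plan says.** **The analysis.** Section 7.2, Secondary Hypothesis 1 (printed under the Handling of Missing Data heading), expects that progression judged by "comparing baseline brain MRI and MRI at 12 months will be less for IDH-mutants". Differences and change are to be tested by chi-square and Student t-test at P < 0.05. No progression event, slope, repeated-measures model or time-to-event analysis is defined.

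**The scans.** The Schedule of Events marks the anatomical MRI at baseline and at Days 90, 180 and 300, and has no 12-month column. Section 6.15 (the Day 300 visit) says only that the MRI is reviewed. Section 3.5 gives two further schedules: "Anatomic brain MRI with perfusion scanning/gadolinium will be obtained at 3 months and then every 3 months, to examine the correlated progression of brain tumor", and later "follow-up brain MRI at 3 months and 6 months during PER use". Footnote 7 of the schedule lets a scan up to three months old serve as baseline.

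**Patients who die.** Section 3.4: "In event of patients not surviving till 12 months, most recent data prior to death will be used for correlation". The same section says "All comparisons will use intent to treat model for patients initiated or exiting PER therapy". Section 7.3 says instead "Analysis of the protocol-compliant population will be conducted", and ties evaluability at 3, 6 and 12 months to disease severity and "risk of imminent death from high-grade malignant primary brain tumor". The text under Handling of Missing Data otherwise covers data entry, checking and the hypotheses, and gives no rule for a missing scan.

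**The concern.** Change between two scans can be measured over the planned interval only in patients who live to the second scan, and the protocol itself expects some not to. Under section 3.4 a patient who dies contributes growth over a shorter interval, set against the full interval in survivors. Under section 7.3 the same patient may not contribute at all, for a reason close to the outcome being measured. Under either rule, death from the tumour is not recorded as progression.

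Progression on perampanel versus alternate ASDs is a secondary objective, and the IDH contrast is a stated hypothesis with a significance threshold. If one group loses more patients early, its progression can look milder than it was. A larger sample would not remove that distortion, and this pilot is meant to inform a larger trial.

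**Working it through.** The plan states no figure to reproduce: it gives no growth rate, SD, death rate or IDH mix. The steps below show how each rule behaves under stated assumptions.

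**1. Which rule applies.** Section 3.4 keeps the patient with the last scan before death. Section 7.3 can remove the patient. The documents do not say which governs the MRI comparison, so both are followed.

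**2. Interval captured by the last scan.** If growth is linear, share of full change = month of last scan before death / month of final scan.

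- Schedule of Events (months 0, 3, 6, 10): death at month 4 gives 3/10 = 30%; at month 7, 6/10 = 60%; at month 9.5, 6/10 = 60%.
- Three-monthly scans to month 12: death at month 4 gives 3/12 = 25%; at month 7, 6/12 = 50%; at month 11, 9/12 = 75%.

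This shortfall does not depend on any link between death and growth.

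**3. Effect on the IDH difference (simulation, all inputs assumed).** There were 400,000 patients per group. Log-volume growth per month *g* was 0.15 (SD 0.10) in wildtype and 0.05 (SD 0.05) in mutant. Scans were at months 0, 3, 6 and 10, with measurement SD 0.1. The true 10-month difference is 10 × (0.15 − 0.05) = 1.00. The monthly death hazard was h0·exp(*g*·t) with a link to growth, or constant at h0 without one; h0 in mutant was one third of that in wildtype. The last-scan column uses patients with at least one follow-up scan.

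| Link | h0 (wildtype) | Dead by month 10, wildtype / mutant | Survivors only | Last scan before death |
|---|---|---|---|---|
| Yes | 0.01 | 24% / 4% | 0.84 | 0.79 |
| Yes | 0.02 | 40% / 9% | 0.72 | 0.66 |
| Yes | 0.03 | 52% / 13% | 0.62 | 0.56 |
| No | 0.01 | 10% / 3% | 1.00 | 0.95 |
| No | 0.02 | 18% / 6% | 1.00 | 0.91 |
| No | 0.03 | 26% / 10% | 1.00 | 0.87 |

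The no-link rows also have fewer deaths, because the hazard no longer rises with volume (for example 1 − exp(−0.01 × 10) = 10%). The two blocks therefore differ in death rate as well as in the link.

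**4. A second model as a check.** Here growth was linear, 2 units per month in wildtype and 1 in mutant (coefficient of variation 0.5). Median survival was 10 to 18 months and 24 to 36 months respectively. The log-hazard slope on standardised log growth was 0, 0.5 or 1.0.

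- Scans to month 12: a true difference of 12.0 becomes 7.3 to 12.0 in survivors and 5.5 to 9.4 with the last scan.
- Scans to month 10: 10.0 becomes 6.4 to 10.1 in survivors (the excess over 10.0 is simulation error) and 5.0 to 8.2 with the last scan.
- With a link, the fastest-growing quarter of wildtype patients makes up 5 to 18% of completers instead of 25%.

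No scenario in either model reverses the sign.

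**5. How many patients.** If 10% die before the last scan, 2 of 20 are expected, and the chance of at least one is 1 − 0.9^20 = 88%. At 50%, 10 of 20 are expected.

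**The case against.** **Section 3.4 already has a rule for death.** It does, and if it governs the MRI comparison, a Day 90 or Day 180 scan would stand in as the last one. A reader might infer that those scans are never used; the documents do not support that. What stands is that no analysis uses them as a series, and that substituting one shortens the interval without adjustment.

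**Dropping patients need not bias anything.** This is correct if death is unrelated to growth: survivors then give 1.00. Section 7.3 makes a link plausible by naming severity and imminent tumour death together, but gives no strength for it.

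**Deaths are counted elsewhere.** Overall survival is listed in section 3.4, but only at 3 months and only for perampanel-treated patients. It does not repair the progression comparison.

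**At this size noise exceeds bias.** Section 7.1 calls this an unpowered pilot of 20, and the hypothesis refers to two perampanel doses, so it may concern only the 10 perampanel patients. With an assumed 5 versus 5 IDH split and all ten scanned, the SD of the step 3 difference is √[(1.02 + 0.27)/5] = 0.51, where 1.02 = (10 × 0.10)² + 2 × 0.1² and 0.27 = (10 × 0.05)² + 2 × 0.1². Once deaths thin the groups it is about 0.57 to 0.68. The linked survivor-only bias is 0.16 to 0.38. This limits the priority of the point. It does not make a distorted endpoint a good one to carry into a larger trial.

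**Conclusion.** The point holds at moderate priority. The plan states a concrete two-scan analysis, anchors it to an MRI the Schedule of Events does not contain, and has two incompatible rules for early death, neither of which treats death as progression.

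Carrying the last scan forward understates change in growing tumours of patients who die, whether or not death is linked to growth. Dropping those patients biases the comparison only if death is linked to growth. In the main simulation the IDH difference shrinks by 0 to 38% in survivors only and by 5 to 44% with the last scan. These sizes rest wholly on assumed growth and death rates, including faster growth and more deaths in wildtype.

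A reader might go further and infer that a real difference could be reversed. No scenario showed that. Nor can a direction be given for perampanel versus alternate ASDs: it depends on which arm has more early deaths, the treating physician chooses the arm (section 4.3), and no between-arm calculation was made.

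**What to change.** **In section 7.2**, replace the two-scan change with time from Day 0 to first progression on any scheduled MRI (Days 90, 180, 300) or death, whichever comes first. Include all enrolled patients, and censor those alive without progression at their last MRI. Show Kaplan-Meier curves by arm and by IDH status with 95% CIs, labelled descriptive because N = 20. Deaths before the first follow-up scan then count.

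**Reconcile** the 12-month wording with the Day 300 schedule, with section 6.15 and with both MRI schedules in section 3.5. Reconcile the intent-to-treat and last-data rules of section 3.4 with the protocol-compliant and evaluability text of section 7.3.

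**Report tumour volume** descriptively as a rate per month from all scans, using actual scan dates because the baseline MRI may be up to three months old. Use a scale that allows zero volume, since section 3.5 foresees absence of tumour and a logarithm fails there. A rate alone is not enough: in the second model it still understated wildtype growth by 0 to 13%, because patients who die before the first follow-up scan are missing.

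**Cost:** SAP wording and modest analysis time, with no scans beyond the Schedule of Events. One definition of progression must be fixed before the data are read, and the curves will be imprecise.
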